10.1.3. Data Protection

Patients will be assigned a unique identifier by the sponsor. Any patient records or datasets that are transferred to the sponsor will contain the identifier only; patient names or any information which would make the patient identifiable will not be transferred.

The patient must be informed that his/her personal study-related data will be used by the sponsor in accordance with local data protection law. The level of disclosure must also be explained to

the patient who will be required to give consent for their data to be used as described in the informed consent.

The patient must be informed that his/her medical records may be examined by Clinical Quality Assurance auditors or other authorized personnel appointed by the sponsor, by appropriate IRB/IEC members, and by inspectors from regulatory authorities.

10.1.4. Dissemination of Clinical Study Data

A clinical study report (CSR) will be prepared and provided to the regulatory agency(ies) by Terns, as appropriate. Terns will ensure that the report meets the standards set out in the ICH Guideline for Structure and Content of Clinical Study Reports (ICH E3). Note that an abbreviated report may be prepared in certain cases. Public disclosure of study results will be in accordance with all applicable laws and ICH guidelines. The posting of company-sponsored study information and tabular study results may be presented on the US National Institutes of Health's website www.ClinicalTrials.gov and other publicly accessible sites.

10.1.5. Data Quality Assurance

All patient data relating to the study will be recorded on printed or electronic CRF unless transmitted to the sponsor or designee electronically (e.g., laboratory data). The Investigator is responsible for verifying that data entries are accurate and correct by physically or electronically signing the CRF.

The Investigator must maintain accurate documentation (source data) that supports the information entered in the eCRF.

The Investigator must permit study-related monitoring, audits, IRB/IEC review, and regulatory agency inspections and provide direct access to source data documents.

Monitoring details describing strategy (e.g., risk-based initiatives in operations and quality such as Risk Management and Mitigation Strategies and Analytical Risk-Based Monitoring), methods, responsibilities and requirements, including handling of noncompliance issues and monitoring techniques (central, remote, or on-site monitoring) are available in the Monitoring Plan and site-specific contracts.

The sponsor or designee is responsible for the data management of this study including quality checking of the data.

The sponsor assumes accountability for actions delegated to other individuals (e.g., Contract Research Organizations).

Study monitors will perform ongoing source data verification to confirm that data entered into the eCRF by authorized site personnel are accurate, complete, and verifiable from source documents; that the safety and rights of patients are being protected; and that the study is being conducted in accordance with the currently approved protocol and any other study agreements, ICH GCP, and all applicable regulatory requirements.

Records and documents, including signed ICFs, pertaining to the conduct of this study must be retained by the Investigator until at least 2 years after the last approval of a marketing application in an ICH region (i.e., United States, Europe, or Japan) and until there are no pending or contemplated marketing applications in an ICH region (i.e., United States, Europe, or Japan) or at least 2 years have elapsed since the formal discontinuation of clinical development of the investigational product. These documents should be retained for a longer period however if required by the applicable regulatory requirement(s) or if needed by the sponsor. No records may be destroyed during the retention period without the written approval of the sponsor. No records may be transferred to another location or party without written notification to the sponsor.

10.1.6. Protocol Deviations

Prospective approval of protocol deviations to recruitment and enrollment criteria, also known as protocol waivers or exemptions, is not permitted. In the event of a significant deviation related to gross non-compliance from the protocol, or events that impose significant risk to patient safety, the Investigator or designee must notify the Sponsor or designee immediately. Deviations must be documented in accordance with the Sponsor's procedures, and in accordance with any site procedures or processes.

10.1.7. Source Documents

Source documents provide evidence for the existence of the patient and substantiate the integrity of the data collected. Source documents are stored at the Investigator's site.

Data reported on the eCRF or entered in the eCRF that are transcribed from source documents must be consistent with the source documents or the discrepancies must be explained. The Investigator may need to request previous medical records or transfer records, depending on the study.

The required source data should include notes containing at least the following information for each patient:

- Patient identification (name, date of birth, gender)
- Documentation that the patient meets eligibility criteria

- Documentation of the reason(s) a consented patient is not enrolled
- Participation in study (including study number)
- Study discussed and date of informed consent
- Dates of all visits
- Documentation that protocol specific procedures were performed
- Results of efficacy parameters, as required by the protocol
- Start and end date (including dose regimen) of study drug administration, including dates of dispensation and return as applicable
- Record of all adverse events and other safety parameters (start and end date, and including causality and severity)
- Concomitant medication (including start and end date, dose if relevant; dose changes)
- Date of study completion and reason for early discontinuation, if applicable

10.1.8. Study and Site Start and Closure

The first patient screened is considered the first act of recruitment and will be the study start date.

The sponsor or designee reserves the right to close the study site or terminate the study at any time for any reason at the sole discretion of the sponsor. Study sites will be closed upon study completion. A study site is considered closed when all required documents and study supplies have been collected and a study-site closure visit has been performed.

The Investigator may initiate study-site closure at any time, provided there is reasonable cause and sufficient notice is given in advance of the intended termination.

Reasons for the early closure of a study site by the sponsor or Investigator may include but are not limited to:

- Failure of the Investigator to comply with the protocol, the requirements of the IRB/IEC or local health authorities, the sponsor's procedures, or GCP guidelines
- Inadequate recruitment of patients by the Investigator
- Discontinuation of further study drug development

If the study is prematurely terminated or suspended, the sponsor shall promptly inform the Investigators, the IECs/IRBs, the regulatory authorities, and any contract research

organization(s) used in the study of the reason for termination or suspension, as specified by the applicable regulatory requirements. The Investigator shall promptly inform the patient and should assure appropriate follow-up care as warranted by the protocol or as medically necessary.

Appendix 1: Clinical Laboratory Tests

The tests detailed in [Table 2](#) will be performed by the central laboratory. Local laboratory testing should only be used in the event that central laboratory results would not available in time for necessary clinical decision making. If a local sample is required, it is important that a sample for central analysis is obtained at the same time. Additionally, if the local laboratory results are used to make either a study drug decision or response evaluation, the results must be entered into the eCRF.

Protocol-specific requirements for inclusion or exclusion of patients are detailed in [Section 5](#). Additional tests may be performed at any time during the study as determined necessary by the Investigator or required by local regulations.

Table 2 **Protocol-Required Clinical Laboratory Assessments**

Laboratory Assessments	Parameters	
Hematology	Hematocrit Hemoglobin Hemoglobin A1c ¹ Platelet Count RBC Count RBC Indices: 
• MCV• MCH• MCHC• % Reticulocytes	WBC count with Differential: 
• Neutrophils• Lymphocytes• Monocytes• Eosinophils• Basophils
Clinical Chemistry ²	Bicarbonate BUN Calcium Chloride CPK Creatinine eGFR ³ Glucose Phosphorus Potassium Sodium	Liver Function Tests: 
• ALT• Albumin• AST• ALP• GGT• Total and Direct Bilirubin⁴

Laboratory Assessments	Parameters
	Total Protein
Coagulation ⁵	aPTT ¹ PT/INR
Fasting Lipid Profile	HDL LDL Total Cholesterol Triglycerides VLDL
Urinalysis	
 Specific gravity pH, glucose, protein, albumin, creatinine, blood, ketones, bilirubin, urobilinogen, nitrite, leukocyte esterase by dipstick, UPCR, and UACR Microscopic examination (if blood or protein is abnormal)
Pregnancy	Highly sensitive serum β -hCG (WOCBP only)
Other Tests	
 FSH (to confirm post-menopausal status)¹ Blood alcohol test¹ Urine drug screen including amphetamines, barbiturates, cocaine, opiates, cannabinoids and benzodiazepines Serology¹: HIV antibody, HBsAg, and HCV antibody⁶ COVID-19: SARS-CoV-2 test for active infection (e.g., molecular test such as PCR or viral antigen serology), and SARS-CoV-2 Ab test (IgG and IgM)
NOTES:	
¹ Only collected at Screening.	
² Details of liver chemistry increased monitoring criteria are given in Appendix 3 .	
³ eGFR to be calculated by central lab; refer to Appendix 5 for the formula.	
⁴ If total bilirubin is increased above the upper limit of normal there should be a reflex to direct and indirect bilirubin, as outlined in Appendix 3 .	
⁵ At Screening, Week 0, and if significant abnormal liver function is observed, as outlined in Appendix 3 .	
⁶ If HCV antibody positive, conduct HCV RNA test.	

Abbreviations: ALP = alkaline phosphatase; ALT = alanine transaminase; AST = aspartate transaminase; aPTT = activated partial thromboplastin time; β -hCG = β -human chorionic gonadotropin; BUN = blood urea nitrogen; CPK = creatine phosphokinase; eGFR = estimated glomerular filtration rate; FSH = Follicle-stimulating hormone; GGT = gamma-glutamyl transpeptidase; HbA1c = hemoglobin A1c; HBsAg = hepatitis B surface antigen; HCG = human chorionic gonadotropin; HCV = hepatitis C virus; HDL = high-density lipoprotein; HIV = human immunodeficiency virus; IgG = immunoglobulin G; IgM = immunoglobulin M; INR = international normalized ratio; LDL = low-density lipoprotein; MCH = mean corpuscular hemoglobin; MCHC = mean corpuscular hemoglobin concentration; MCV = mean corpuscular volume; PCR = polymerase chain reaction; PT =

prothrombin time; RBC = red blood cell; RNA = ribonucleic acid; SARS-CoV-2 = Severe Acute Respiratory Syndrome Coronavirus 2; UACR = urine albumin:creatinine ratio; UPCR = urine protein:creatinine ratio; VLDL = very low-density lipoprotein; WBC = white blood cell; WOCBP = women of childbearing potential

Investigators must document their review of each laboratory safety report. Clinically significant laboratory shifts, or any clinically significant abnormalities considered possibly related to study drug in the opinion of the Investigator, should be repeated within 48-72 hours and followed to resolution or until stable.

Appendix 2: Sample Collection for Pharmacokinetics and Pharmacodynamics

[Table 3](#) presents a description of PK/PD sample requirements at each study visit and timepoint.

Table 3 PK/PD Sampling Timepoints

Week	Day	Timepoint
0 ¹	1	
• Pre-dose (All Patients)• Post dose at the following timepoints (PK/PD sub-study only):
○ 30 ± 2 minutes○ 1 hour ± 5 minutes○ 2 hours ± 5 minutes○ 4 hours ± 15 minutes○ 6 hours ± 15 minutes○ 8 hours ± 30 minutes• Total urine collection from 0-8 hours post dose (PK/PD sub-study only)
0	2	
• Post Day 1 dose at the following timepoint (PK/PD sub-study only):
○ 24 hours ± 1 hour
2	15 ± 3	
• Pre-dose (All Patients)
4	29 ± 3	
• Pre-dose (All Patients)
6	43 ± 3	
• Pre-dose (All Patients)• Post dose at the following timepoints (PK/PD sub-study only):
○ 30 ± 2 minutes○ 1 hour ± 5 minutes○ 2 hours ± 5 minutes○ 4 hours ± 15 minutes○ 6 hours ± 15 minutes○ 8 hours ± 30 minutes• Total urine collection from 0-8 hours post dose (PK/PD sub-study only)
6	44	
• Post Week 6 dose at the following timepoint (PK/PD sub-study only):
○ 24 hours ± 1 hour
8	57 ± 3	
• Pre-dose (All Patients)

Week	Day	Timepoint
12	85 ± 3	
• Pre-dose (All Patients)• Post dose at the following timepoints (PK/PD sub-study only):
○ 30 ± 2 minutes○ 1 hour ± 5 minutes○ 2 hours ± 5 minutes○ 4 hours ± 15 minutes○ 6 hours ± 15 minutes○ 8 hours ± 30 minutes
12	86	
• Post Week 12 dose at the following timepoint (PK/PD sub-study only):
○ 24 hours ± 1 hour
12	87	
• Post Week 12 dose at the following timepoint (PK/PD sub-study only):
○ 48 hours ± 2 hours
12	88	
• Post Week 12 dose at the following timepoint (PK/PD sub-study only):
○ 72 hours ± 4 hours
ET	ET	
• At the ET Visit, for all patients discontinuing the study at any time for any reason prior to Week 12

NOTES:

¹ sVAP-1 will be collected along with PD sampling at Week 0/Day 1 pre-dose.

Abbreviations: ET = early termination; PD = pharmacodynamics; PK = pharmacokinetics; sVAP-1 = soluble vascular adhesion protein-1

Appendix 3: Liver Chemistry Increased Monitoring Criteria

[Table 4](#) summarizes requirements for follow-up of liver function test abnormalities.

Table 4 Liver Chemistry Increased Monitoring Criterion and Follow-Up

Criterion	Actions
Elevated ALT and/or AST above 2 × Baseline or above 5 × ULN for < 1 week	
• Patient can continue study drug at the discretion of the Investigator• Repeat measurement of LFTs (including ALT, AST, ALP, and total bilirubin) will be performed within 48-72 hours to confirm the abnormalities and to determine if they are increasing or decreasing. If total bilirubin is increased there should be a reflex to direct and indirect bilirubin.• PT/INR and albumin will be tested when significantly abnormal liver function is observed, and repeated with repeat measurement of LFTs.• Upon confirmation of elevated LFTs, close observation by repeating LFTs every 24 to 72 hours will be initiated immediately.• Frequency of monitoring can be decreased as LFTs decrease at the Investigator's discretion.• The Investigator will collect detailed history information on concomitant symptoms, new medications, drug or alcohol exposure, etc., to identify possible cause of abnormal LFTs.• Close observation on abnormal LFTs will last until the parameters return to baseline, or to a stable level judged by the Investigator.

Note: If one of the following situations occurs and is considered related to the study drug without alternative etiology, study drug may be discontinued at the discretion of the Investigator and the Medical Monitor should be informed (with repeat test performed within 48-72 hours once initial abnormality is detected):
 
• ALT or AST > 8 × ULN• ALT or AST > 5 × ULN for more than 1 week• ALT or AST > 2 × Baseline with the appearance of fatigue, nausea, vomiting, right upper quadrant pain or tenderness, fever, rash, and/or eosinophilia (> 5%)• ALT or AST > 2 × Baseline and total bilirubin > 2 × ULN or INR > 1.5 for more than 1 week, confirmed with a repeat assessment	

Abbreviations: ALP = alkaline phosphatase; ALT = alanine transaminase; AST = aspartate transaminase; INR = international normalized ratio; LFT = liver function test; PT = prothrombin time; ULN = upper limit of normal

Appendix 4: Fridericia's Formula

A single 12-lead ECG will be obtained as outlined in the Schedule of Activities (see [Section 1.3](#)) using an ECG machine that automatically calculates the heart rate and measures PR, QRS, and QT intervals. QTc will be calculated using Fridericia's Formula as outlined below.

The Investigator will review the ECGs for any clinically significant abnormalities.

Fridericia's Formula:

$$QTcF = QT / (RR^{0.33})$$

<http://www.thecalculator.co/health/QTc-Calculator-385.html>

Appendix 5: Chronic Kidney Disease Epidemiology Collaboration (CKD-EPI) Formula to Estimate Glomerular Filtration Rate

$$\text{GFR} = 141 \times \min(S_{\text{Cr}}/\kappa, 1)^\alpha \times \max(S_{\text{Cr}}/\kappa, 1)^{-1.209} \times 0.993^{\text{Age}} \times 1.018 \text{ [if female]} \times 1.159 \text{ [if black]}$$

Abbreviations / Units:

SCr (standardized serum creatinine) = mg/dL

κ = 0.7 (females) or 0.9 (males)

α = -0.329 (females) or -0.411 (males)

min = indicates the minimum of SCr/ κ or 1

max = indicates the maximum of SCr/ κ or 1

age = years

Appendix 6: Adverse Events: Definitions and Procedures for Recording, Evaluating, Follow-up, and Reporting

AE Definition

- An AE is any untoward medical occurrence in a patient or clinical study patient, temporally associated with the use of study drug, whether or not considered related to the study drug.
- NOTE: An AE can therefore be any unfavorable and unintended sign (including an abnormal laboratory finding), symptom, or disease (new or exacerbated) temporally associated with the use of study drug.

Events Meeting the AE Definition

- Any safety assessment (e.g., ECG, radiological scans, vital signs measurements), including those that worsen from baseline, considered clinically significant in the medical and scientific judgment of the Investigator (i.e., not related to progression of underlying disease).
- A clinical condition or symptom associated with an abnormal laboratory test result (e.g., hematology, clinical chemistry, or urinalysis). An abnormal laboratory test that is not accompanied with other signs or symptoms should not be reported as an AE.
- Exacerbation of a chronic or intermittent pre-existing condition including either an increase in frequency and/or severity of the condition.
- New conditions detected or diagnosed after study drug administration even though it may have been present before the start of the study.
- Signs, symptoms, or the clinical sequelae of a suspected drug-drug interaction.
- Signs, symptoms, or the clinical sequelae of a suspected overdose of either study drug or a concomitant medication. Overdose per se will not be reported as an AE/SAE unless it is an intentional overdose taken with possible suicidal/self-harming intent. Such overdoses should be reported regardless of sequelae.

Events NOT Meeting the AE Definition

- Abnormal laboratory findings or other abnormal safety assessments that are associated with an underlying disease present at baseline without worsening, unless judged by the Investigator to be more severe than expected for the patient's condition.
- An abnormal laboratory test that is not accompanied with other signs or symptoms.
- The disease/disorder being studied or signs, or symptoms of the disease/disorder being studied, unless more severe than expected for the patient's condition.
- Medical or surgical procedure (e.g., endoscopy, appendectomy): the condition that leads to the procedure is the AE.
- Situations in which an untoward medical occurrence did not occur (social and/or convenience admission to a hospital).
- Anticipated day-to-day fluctuations of pre-existing disease(s) or condition(s) present or detected at the start of the study that do not worsen.

Definition of SAE

An SAE is an AE that meets the following criteria:

An SAE is defined as any untoward medical occurrence that, at any dose:

a. Results in death

b. Is life-threatening

The term 'life-threatening' in the definition of 'serious' refers to an event in which the patient was at risk of death at the time of the event. It does not refer to an event, which hypothetically might have caused death, if it were more severe.

c. Requires inpatient hospitalization or prolongation of existing hospitalization

- In general, hospitalization signifies that the patient has been detained (usually involving at least an overnight stay) at the hospital or emergency ward for observation and/or treatment that would not have been appropriate in the physician's office or outpatient setting. Complications that occur during hospitalization are AEs. If a complication prolongs hospitalization or fulfills any other serious criteria, the event is serious. When in doubt as to whether "hospitalization" occurred or was necessary, the AE should be considered serious.
- Hospitalization for elective treatment of a pre-existing condition that did not worsen from baseline is not considered an AE.

d. Results in persistent disability/incapacity

- The term disability means a substantial disruption of a person's ability to conduct normal life functions.
- This definition is not intended to include experiences of relatively minor medical significance such as uncomplicated headache, nausea, vomiting, diarrhea, influenza, and accidental trauma (e.g., sprained ankle) which may interfere with or prevent everyday life functions but do not constitute a substantial disruption.

e. Is a congenital anomaly/birth defect

f. Other situations:

- Medical or scientific judgment should be exercised in deciding whether SAE reporting is appropriate in other situations such as important medical events that may not be immediately life-threatening or result in death or hospitalization but may jeopardize the patient or may require medical or surgical intervention to prevent one of the other outcomes listed in the above definition. These events should usually be considered serious.
- Examples of such events include invasive or malignant cancers, intensive treatment in an emergency room or at home for allergic bronchospasm, blood dyscrasias or convulsions that do not result in hospitalization, or development of drug dependency or drug abuse.

If an event does not meet the AE definition, then it cannot be an SAE even if serious conditions are met (e.g., hospitalization for signs/symptoms of the disease under study, death due to progression of disease).

Recording and Follow-Up of an AE and/or SAE

AE and SAE Recording

- When an AE and/or SAE occurs, it is the responsibility of the Investigator to review all documentation (e.g., hospital progress notes, laboratory reports, and diagnostics reports) related to the event.
- The Investigator will then record all relevant AE and/or SAE information in the eCRF.
- It is **not** acceptable for the Investigator to send photocopies of the patient's medical records to the Sponsor or designee in lieu of completion of the AE or SAE eCRF.
- There may be instances when copies of medical records for certain cases are requested by the Sponsor or designee. In this case, all patient identifiers, with the exception of the patient number, will be redacted on the copies of the medical records before submission to the Sponsor or designee.

- The Investigator will attempt to establish a diagnosis of the event based on signs, symptoms, and/or other clinical information. Whenever possible, the diagnosis (not the individual signs/symptoms) will be documented as the AE and/or SAE.

Assessment of Severity

The Investigator will be asked to provide an assessment of the severity of the AE using NCI CTCAE v5.0 categories as follows:

- Grade 1: Mild; asymptomatic or mild symptoms; clinical or diagnostic observations only; intervention not indicated.
- Grade 2: Moderate; minimal, local, or noninvasive intervention indicated; limiting age appropriate instrumental ADL.
- Grade 3: Severe or medically significant but not immediately life-threatening; hospitalization or prolongation of hospitalization indicated; disabling; limiting self-care ADL.
- Grade 4: Life-threatening consequences; urgent intervention indicated.
- Grade 5: Death related to AE.

For detailed organ system AE severity grading, please refer to NCI CTCAE v5.0:

https://ctep.cancer.gov/protocoldevelopment/electronic_applications/docs/CTCAE_v5_Quick_Reference_8.5x11.pdf

Assessment of Causality

- The Investigator is obligated to assess the relationship between study drug and each occurrence of each AE and/or SAE.
- The Investigator (or designee) will make a determination of the relationship of the AE to the study drug using a 4-category system according to the following guidelines:
 - **Not Related:** The AE is definitely caused by the subject's clinical state or the study procedure/conditions.
 - **Unlikely Related:** The temporal association between the AE and the drug is such that the drug is not likely to have any reasonable association with the AE.
 - **Possibly Related:** The AE follows a reasonable temporal sequence from the time of drug administration but could have been produced by the subject's clinical state or the study procedures/conditions.
 - **Related:** The AE follows a reasonable temporal sequence from administration of the drug, abates upon discontinuation of the drug, follows a known or hypothesized cause effect relationship, and (if appropriate) reappears when the drug is reintroduced.
- For each AE and/or SAE, the Investigator **must** document in the medical notes that he/she has reviewed the AE and/or SAE and has provided an assessment of causality.
- There may be situations in which an SAE has occurred and the Investigator has minimal information to include in the initial report to the Sponsor or designee. However, it is very important that the Investigator always make an assessment of

causality for every event before the initial transmission of the SAE data to the Sponsor or designee.

- The Investigator may change his/her opinion of causality in light of follow-up information and send a SAE follow-up report with the updated causality assessment.
- The causality assessment is one of the criteria used when determining regulatory reporting requirements.

Follow-up of AEs and SAEs

- The Investigator is obligated to perform or arrange for the conduct of supplemental measurements and/or evaluations as medically indicated or as requested by the Sponsor or designee to elucidate the nature and/or causality of the AE or SAE as fully as possible. This may include additional laboratory tests or investigations, histopathological examinations, or consultation with other health care professionals.
- If a patient dies during participation in the study or during a recognized follow-up period, the Investigator will provide the Sponsor or designee with a copy of any post-mortem findings including histopathology.
- New or updated information will be recorded in the originally completed CRF.
- The Investigator will submit any updated SAE data to the Sponsor or designee within 24 hours of receipt of the information.

Reporting of SAEs

SAE Reporting to Sponsor or designee via Paper CRF

- Email transmission of the SAE paper Report Form is the preferred method to transmit this information to the CATO Safety Group ([contact]).
- Notification by facsimile transmission to the CATO Safety Group is also acceptable [contact])
- Initial notification via telephone or email does not replace the need for the Investigator to complete, sign, and return the SAE report form within the designated reporting time frames.
- Contacts and additional instructions for SAE reporting can be found in the Study Procedures Manual provided.

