8.1.7. Clinical Laboratory Assessments

See [Appendix 1](#) for the list of clinical laboratory tests to be performed and the Schedule of Activities for the timing and frequency.

The Investigator must review the laboratory report, document this review, and record any AEs per the guidance in [Appendix 6](#). The laboratory reports must be filed with the source documents.

Clinically significant laboratory shifts, or any clinically significant abnormalities considered possibly related to study drug in the opinion of the Investigator, should be repeated within 48-72 hours and followed to resolution or until stable.

All protocol-required laboratory assessments, as defined in [Appendix 1](#), must be conducted in accordance with the laboratory manual and the Schedule of Activities.

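### Appendix 6 of the protocol twice bars symptom-free laboratory abnormalities from AE reporting with no exception, so a drug-attributed enzyme rise that stops treatment can be left out of the TEAE tables at one site and recorded at another

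*Protocol*

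**What the plan says.** Protocol Section 8.1.7 sends sites to Appendix 6 for laboratory AEs: "The Investigator must review the laboratory report, document this review, and record any AEs per the guidance in" that appendix. It gives no other rule.

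Appendix 6 then says several things:

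- The NOTE under the AE definition: "An AE can therefore be any unfavorable and unintended sign (including an abnormal laboratory finding), symptom, or disease".
- Under events that meet the definition: "Any safety assessment (e.g., ECG, radiological scans, vital signs measurements), including those that worsen from baseline, considered clinically significant" in the Investigator's judgment.
- The next bullet in that list: "An abnormal laboratory test that is not accompanied with other signs or symptoms should not be reported as an AE".
- Under events that do not meet the definition, as a bullet of its own: "An abnormal laboratory test that is not accompanied with other signs or symptoms".
- On seriousness: "If an event does not meet the AE definition, then it cannot be an SAE even if serious conditions are met".

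Section 7.1 and Appendix 3 list liver criteria under which study drug may be stopped at the Investigator's discretion if the rise is attributed to the drug and no other cause is found. Two of them, ALT or AST above 8 × ULN and above 5 × ULN for more than a week, need no symptom. Section 7.1 separately makes stopping mandatory for a related AE of Grade 3 or above.

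SAP Section 9.2 limits AE summaries to TEAEs. SAP Section 9.2.2 takes the leading-to-discontinuation table from recorded AEs whose action taken is drug withdrawal.

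**The concern.** The protocol foresees symptom-free, drug-attributed enzyme rises large enough to stop treatment, and in the same document tells sites not to report isolated laboratory abnormalities as AEs. TEAEs are one of the two components of the primary endpoint. The AE record is also where the Investigator's causality judgment, the severity grade and the action taken with study drug are captured for the TEAE tables.

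Three things depend on whether the event counts as an AE: its place in the TEAE tables, whether it can be an SAE subject to 24-hour reporting, and whether a related Grade 3 or higher event triggers the mandatory stop or only the discretionary liver criteria. With up to 15 centers and arms of about 20, sites that read Appendix 6 differently would report the same event differently.

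**Working it through.** No figure in the plan needs reproducing, because the point is textual. The check has three steps.

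**1. Do the Appendix 6 statements agree?**

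| Statement in Appendix 6 | Effect on an isolated laboratory abnormality |
|---|---|
| NOTE under the AE definition | Can be an AE |
| Clinical-significance bullet | Can be an AE if laboratory tests count as safety assessments |
| Next bullet in the same list | Not to be reported as an AE; no exception |
| Stand-alone bullet in the list of non-AEs | Not an AE; no exception |

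The clinical-significance bullet gives ECGs, scans and vital signs only as examples. A bullet in the list of non-AEs groups laboratory findings with other abnormal safety assessments, so reading laboratory tests into the clinical-significance bullet is reasonable. That same bullet has an exception for findings worse than expected for the patient. The exception belongs to findings tied to disease present at baseline; the stand-alone bullet has none.

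**2. Trace one event: symptom-free ALT above 8 × ULN, attributed to study drug, drug stopped.**

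- *Site following the two sentences:* no AE record, therefore no SAE. The patient is absent from the related and leading-to-discontinuation TEAE tables, and from the Grade 3 or higher and serious tables if those criteria were met.
- *Site relying on the NOTE, the clinical-significance bullet, the new-conditions bullet ("New conditions detected or diagnosed after study drug administration even though it may have been present before the start of the study") or the recording instruction ("Whenever possible, the diagnosis (not the individual signs/symptoms) will be documented as the AE and/or SAE"):* the event is recorded and enters those tables.
- *Both sites:* the value is graded from laboratory data (SAP 9.3.1, where a worsening of at least 2 grades is tabulated, and SAP 9.3.3). Any Appendix 3 or modified Hy's rule criterion that is met is listed (SAP 9.3.2). The stop is counted in disposition with its reason (SAP 7.1).

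**3. Size, for illustration.** The protocol plans 20 patients per dose, so 3 × 20 = 60 in the All TERN-201 column if both Part 2 doses enroll.

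- One unrecorded stop: 1/20 = 5.0% becomes 0/20; 1/60 = 1.7% becomes 0/60.
- Two unrecorded stops in one arm: 2/20 = 10.0% becomes 0/20; 2/60 = 3.3% becomes 0/60.

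Let *p* be the true rate of such stops and *s* the share of patients at sites that follow the two sentences. Neither is in the documents; both are assumptions. The chance that an arm of 20 loses at least one event is 1 − (1 − *p* × *s*)^20. For example, *p* = 0.05 and *s* = 0.50 give 1 − 0.975^20 = 0.397.

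| *s* | *p* = 2% | *p* = 5% | *p* = 10% |
|---|---|---|---|
| 25% | 10% | 22% | 40% |
| 50% | 18% | 40% | 64% |
| 100% | 33% | 64% | 88% |

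The last row describes under-recording at every site, not disagreement between sites.

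**The case against.** The best defense is that the NOTE only permits a laboratory finding to be an AE and the lists narrow it. The rule appears in both lists, which suggests a deliberate convention, and laboratory abnormalities have their own component of the primary endpoint. This explains why a sponsor might want such a rule. It does not reconcile the rule with the clinical-significance bullet, and it is hard to square with SAP Section 9.4, which treats clinically significant vital-sign abnormalities as AEs.

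A second argument is that a rise attributed to drug after repeat testing and a search for other causes is close to a diagnosis, which Appendix 6 asks sites to record. This stands in part: Appendix 6 does offer routes to an AE record, so not every site would omit the event. But those routes compete with two sentences that address laboratory tests directly.

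A third is rarity. The first-in-human study had no notable laboratory findings and no AE that led to discontinuation. That is fair, though it concerned healthy participants dosed for at most 14 days, and it is a reason to treat the table of chances as illustration only.

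A reader might go further and infer that the liver signal vanishes from the trial. The documents do not support that. The laboratory, liver-criteria and disposition outputs keep it, Section 7.1 says the Medical Monitor should be informed, and the safety analysis is descriptive with no hypothesis test to distort.

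**Conclusion.** The point holds as a defect in a stated rule. Two unqualified sentences in Appendix 6 conflict with the NOTE and with a reasonable reading of the clinical-significance bullet. At a site that follows them, a drug-attributed enzyme rise that stops treatment goes missing from the AE and SAE records and the TEAE tables built from them. The effect is confined to those records and tables and, through AE status, to which Section 7.1 stopping rule applies.

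Confidence in the textual conflict is high. How often it would matter is unknown: it needs such an event, at a site that reads the sentences literally, with no diagnosis recorded instead. If it happens, one patient moves an arm's TEAE-discontinuation rate by 5.0 percentage points. Whether a given rise reaches Grade 3 depends on CTCAE liver thresholds that neither document reproduces, so the effect on the Grade 3 or higher table and on the mandatory stop is conditional.

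A reader might also infer that enzyme rises recorded as AEs should be exempted from the mandatory stop so that the discretionary liver criteria prevail. The documents do not settle this. Such an exemption would relax a safety rule and is a clinical decision for the sponsor.

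**What to change.** By short protocol amendment, qualify both Appendix 6 sentences in the same words: an isolated laboratory abnormality is not an AE unless the Investigator judges it clinically significant or it leads to interruption or discontinuation of study drug. Meeting a liver monitoring criterion need not by itself make the event an AE.

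In the same amendment the sponsor should state which Section 7.1 rule governs ALT/AST elevations recorded as AEs: the mandatory stop for related events of Grade 3 or above, or the discretionary liver criteria.

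The cost is IRB/IEC approval before implementation (Protocol Section 10.1) and notice to sites, with no new assessments. The price in the data is a few more AE entries and slightly higher TEAE rates. Related laboratory AEs of Grade 3 or above, liver or not, would come under the mandatory stop as Section 7.1 is now written, with resumption possible after discussion with the Medical Monitor and Sponsor. The sponsor should confirm that this is intended.
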